- “Post-Dose 1 and Post-Booster Doses Combined”, which refers to the complete regimen including all the booster doses in Cohort 2a. It includes the 28-day period after each vaccination (dose 1, booster dose 1, and booster dose 2).
- “Post-Dose 1, Post-Dose 2 and Post-Booster Doses Combined”, which refers to the complete regimen including all the booster doses in Cohort 2b. It includes the 28-day period after each vaccination (dose 1, dose 2, booster dose 1, and booster dose 2).

For some tables, e.g. SAE tables, a period “Entire study” will be defined. This will be a combination of all the active phases and periods, so that it covers the time window from vaccination 1 up to and including the end of the study (per participant).

The primary endpoint includes SAEs from the first vaccination until 6 months after completion of the primary regimen for cohorts 2a and 2b. This will be a combined period of post-dose 1 and post-dose 1 Follow Up (FU) (for Cohort 2a) and a combination of post-dose 1, post-dose 1 FU, post-dose 2, and post-dose 2 FU (for Cohort 2b). This period will be labeled “Entire Primary Regimen” or similar in the outputs.

The exploratory endpoints include SAEs from the first booster vaccination time point until the end of the regimen for Cohort 2. This will be a combined period of post-booster 1 until the last follow-up period in Cohorts 2a and 2b. This period will be labeled “Entire Booster Regimen” or similar in the outputs.

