7.3. Primary Endpoint(s) Analysis

The primary endpoints in this study, are:

All participants in Cohorts 1, 2, and 3:

- Solicited local and systemic adverse events (AEs) for 7 days after each vaccination in the primary regimen
- Unsolicited AEs for 28 days after each vaccination in the primary regimen
- For the primary endpoint: Serious adverse events (SAEs) from the first vaccination until 1 year after the second vaccination for Cohorts 1 and 3, and until 6 months after the primary regimen for Cohort 2

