7.6.1. Adverse Events

7.6.2. Definitions

Solicited AEs shown in the tables are extracted from the investigator assessment pages (CE) of the CRF. For unsolicited AEs, only the AEs within the 28-day period following each vaccination will be presented in the safety tables except for SAEs, which will be captured and tabulated in the outputs covering the whole study period. All other collected unsolicited adverse events will be presented through listings.

Solicited administration site symptoms will be considered as related to the study vaccine (by definition).

The severity of the AEs will be classified as grade 1 to 4. Solicited events that are graded less than grade 1, are not considered as AE. In case no grades are available, the grading of the solicited events will occur according to the grading list in Appendix 3.

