7.6.3. Analysis of Adverse Events

Number and percentage of participants with at least one particular AE (unsolicited/solicited) will be tabulated. Unsolicited AEs will be summarized by System Organ Class and Preferred Term. Solicited AEs will be summarized by class (administration site/systemic) and Preferred Term.

For solicited AEs following tables will be provided: summary, by worst severity grade, at least grade 3, related (systemic only), time to onset (in days) and duration (in days) for most frequent events and body temperature. Note: Duration is defined as number of days from the start of the event until resolution of the event. The time to first onset is defined as (date of first onset – reference date + 1). The reference date is the start date of the vaccination period.

^a As indicated previously, all analyses, including the safety analyses, will be conducted by actually received vaccine (“as treated” principle). The sentence “by study intervention regimens as designed per protocol” indicates that the statistical tables are designed with the planned vaccine regimens as columns. Therefore, participants who receive e.g. “Placebo, Placebo” instead of “Ad26.COV2.S 5x10¹⁰ vp, Placebo” will appear in the “Placebo, Placebo” column. However, to avoid sparse columns, participants who receive e.g. “Placebo, Ad26.COV2.S 5x10¹⁰ vp” (which is not a planned vaccine regimen) will be excluded from the statistical tables. They will be included in the listings, as well as in the programmed patient narratives where they will appear as “Subjects with vaccine misallocation”.

For unsolicited AEs, the following tables will be provided: summary table (including SAE, fatal outcome, and discontinuation), all events, most frequent, at least grade 3, permanent stop of vaccine, related, and SAE.

As a general remark, COVID-19 cases will be analyzed separately (see section [7.7.3](#)).

- SAEs that are COVID-19 related will not be included in the SAE tables, but will be included and flagged in the SAE listings. In MedDRA version 23.0, Preferred Terms (PT codes) “COVID-19 (10084268)”, “COVID-19 pneumonia (10084380)”, “Suspected COVID-19” (10084451), “Asymptomatic COVID-19 (10084459)”, “Coronavirus infection” (10051905), “Severe acute respiratory syndrome” (10061982), “SARS-CoV-2 carrier” (10084461), “Exposure to SARS-CoV-2” (10084456), and “Occupational exposure to SARS-CoV-2” (10084394) will be considered COVID-19 related AEs^a.

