The following analyses will be conducted at the time of the End of Study analysis or at an interim analysis^a:

The number and percentage of participants with at least one molecularly confirmed SARS-CoV-2 infection will be tabulated by vaccine regimen, for the entire study period only^b.

The analysis will be repeated pooling all active regimens vs. placebo, where data from all cohorts will be pooled. If at least 5 molecularly confirmed SARS-CoV-2 infection are observed, vaccine efficacy (VE) will be calculated with a 90% confidence interval (CI). Otherwise, no VE will be calculated and only the above mentioned descriptive statistical analysis will be conducted. The following paragraphs provide the rationale for only calculating VE when at least 5 events are observed, as well as the formula to calculate VE and its 90% CI.

Assuming a true VE of 70%, 23 events of molecularly confirmed SARS-CoV-2 infections are required to offer 80% power to detect vaccine efficacy exceeding zero ($H_0: VE = 0$) when using a one-sided alpha level of 0.05 (i.e. a 90% CI) and a randomization ratio of 4.65:1 (860 active:185 placebo). Assuming a true VE of 90%, 5 events are required to offer 80% power to detect vaccine efficacy exceeding zero ($H_0: VE = 0$) when using a one-sided alpha level of 0.05 (i.e. a 90% CI) and a randomization ratio of 4.65:1 (860 active:185 placebo).

^a All or some of the described analyses may also be performed prior to the End of Study analysis, but after the Primary analysis. Since no formal hypothesis tests are performed, no alpha spending will be applied.

^b Note that the observation period ends at the time of unblinding or receipt of an unscheduled vaccine, whichever occurs first, cf. section 9.7 of clinical trial protocol amendment 15. This censoring rule applies to all efficacy analyses.

The formula to calculate VE (as a percentage) is:

$$VE = 100 \times \left(1 - \frac{p}{r(1 - p)}\right)$$

Where p = proportion of events occurring among the group of participants vaccinated with Ad26.COV2.S, r = the ratio of the number participants vaccinated with Ad26.COV2.S to the number of participants vaccinated with placebo. 90% asymptotic Wald confidence limits will be calculated.

The number and percentage of participants with at least one molecularly confirmed Influenza infection will be tabulated by vaccine regimen, for the entire study period only.

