The number and percentage of participants with at least one positive non-S protein ELISA (e.g., N ELISA), if available, will be tabulated by vaccine regimen. The analysis will be repeated pooling all active regimens vs. placebo, where data from all cohorts will be pooled. If at least 5 positive non-S protein ELISA events have been observed, VE can be calculated against this endpoint, using the same approach as outlined above for the VE against molecularly confirmed SARS-CoV-2 infection.

For each participant with confirmed COVID-19 infection, a narrative will be prepared based on the visit performed 28 days after the onset of COVID-19 signs and symptoms and other selected information from the clinical database, as available:

- participant ID
- vaccination regimen
- sex, race, ethnicity, age, BMI, dates at which vaccinations were received
- physical examination findings based on the visit performed 28 days after the onset of COVID-19 signs and symptoms
- vital signs including body temperature based on the visit performed 28 days after the onset of COVID-19 signs and symptoms
- concomitant medications since symptom onset
- Humoral immune responses as collected at the planned time points + those obtained from the blood sample taken on the visit performed 28 days after the onset of COVID-19 signs and symptoms. This information may be presented graphically.

For the analysis of the SIC (Patient Reported Outcomes, PRO) data, the following considerations apply

- An “episode” is defined as a period in which any symptoms are reported on the SIC, starting from the first day on which symptoms were reported until the first day that the PRO was not completed because the symptoms had resolved (this will be indicated in the SDTM data, with reason for not completing the PRO = “Symptoms resolved” (or similar) or death)
- A symptom (e.g. feeling generally unwell, fatigue, physical weakness, cough, etc.) is assumed to be present on each day the associated Yes/No question is answered “Yes” or the associated severity question has a rating > 0 .

- If the PRO was not completed due to the participant being too ill or due to the participant being hospitalized, the symptom will be considered present with severity score 10. If the PRO was not completed due to any other reason, no imputations will be done.

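### SAEs are a primary endpoint with no COVID-19 exception, yet COVID-19-coded SAEs are dropped from the SAE tables and the unconfirmed ones are counted by regimen as SAEs nowhere

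*SAP*

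**What the plan says.** Section 7.3 lists as a primary endpoint "Serious adverse events (SAEs) from the first vaccination until 1 year after the second vaccination for Cohorts 1 and 3", with a shorter window for Cohort 2. Section 7.1.2 repeats the Cohort 2 part: "The primary endpoint includes SAEs from the first vaccination until 6 months after completion of the primary regimen for cohorts 2a and 2b". Neither section excludes COVID-19 events.

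Section 7.6.2 limits the unsolicited AE tables to the 28 days after each vaccination, "except for SAEs, which will be captured and tabulated in the outputs covering the whole study period".

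Section 7.6.3 then makes an exception: "SAEs that are COVID-19 related will not be included in the SAE tables, but will be included and flagged in the SAE listings". COVID-19 related is defined by a list of nine MedDRA Preferred Terms, among them "Suspected COVID-19" and two exposure terms. A footnote lets the Data Presentation Specifications revise the list. The reason for the exception is given just before it: "As a general remark, COVID-19 cases will be analyzed separately", with a reference to section 7.7.3.

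Section 7.7.3 plans this table: "The number and percentage of participants with at least one molecularly confirmed SARS-CoV-2 infection will be tabulated by vaccine regimen". It also plans this one: "The number and percentage of participants with at least one positive non-S protein ELISA (e.g., N ELISA), if available, will be tabulated by vaccine regimen".

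**The concern.** The tables that report the primary SAE endpoint do not report it as defined, and the section that receives the removed events uses a different criterion. Removal depends on how an event was coded. Receipt depends on a positive molecular test or a positive serology. An event that meets the first condition but neither form of the second leaves the SAE count and is not counted as an SAE anywhere else. An event that meets both is counted as an infection, and its seriousness is lost in the tables by regimen.

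At stake is the completeness of the SAE incidence by regimen. If vaccination changes the risk or severity of COVID-19 in either direction, the omission will also differ between arms.

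**Working it through.** The SAP gives no figure to reproduce, because the question is which outputs contain a given event. I traced two kinds of SAE through every planned output.

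**A. SAE coded to a COVID-19 term without molecular confirmation**

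- SAE tables (7.6.3): excluded.
- SAE listings (7.6.3): included and flagged. Listings and/or narratives also cover participants with serious AEs, as appropriate.
- Other unsolicited AE tables (7.6.3: all events, most frequent, at least grade 3, related, stop of vaccine): unsettled for onset within 28 days of a dose. The exclusion names only the SAE tables, and only non-serious COVID-19 events are kept out of the SDTM AE domain. The remark about separate analysis points the other way. For onset after 28 days these tables do not apply (7.6.2).
- Unsolicited AE summary table (7.6.3): it has an SAE line. I take the exclusion to cover that line, since otherwise it would disagree with the SAE table. The SAP does not say.
- Harm monitoring (7.7.2): out, since it covers confirmed cases only.
- Infection table and vaccine efficacy (7.7.3): out, confirmed cases only.
- Non-S ELISA table (7.7.3): counted only if the participant is positive and the assay is available, and then not as an SAE.
- Symptom analyses (7.7.3): out unless influenza is confirmed, and then not as an SAE.

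**B. SAE with molecularly confirmed SARS-CoV-2, coded to a listed term**

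- SAE tables: excluded. SAE listings: included and flagged.
- Infection table (7.7.3): counted as an infection, with no split by seriousness.
- Narrative (7.7.3): prepared for each confirmed case, showing the regimen.
- Harm monitoring (7.7.2): from the third confirmed case, active and placebo are compared with 95% and 80% intervals. The same is done for cases with hospitalization, ICU admission or death. Active regimens are pooled, the unblinded statistician does the work, and any imbalance goes to the DRC.

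**How much of the SAE window lies beyond 28 days**

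Counting from the last primary dose:

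- Cohorts 1 and 3: 365 − 28 = 337 days, and 337 / 365 = 92%.
- Cohort 2, taking 6 months as 183 days (my assumption): 183 − 28 = 155 days, and 155 / 183 = 85%.

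For most of that window, an event of type A has no AE table even on the generous reading.

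**Weight of one event**

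Section 7.7.3 uses 860 active and 185 placebo participants.

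- Placebo: 1 / 185 = 0.54 percentage points.
- Pooled active: 1 / 860 = 0.12 percentage points.

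These are the steps by which the tabulated incidence falls for each participant whose only SAE is removed. They are larger in any single regimen within a cohort, where the denominators are smaller. The SAP gives no basis for the expected number of such events.

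**The case against.** The strongest reply is that nothing is concealed. The separation is announced, the terms are printed, every event is flagged in a listing, and confirmed cases get narratives. COVID-19 is the target disease and an exploratory efficacy endpoint, so keeping it apart from vaccine safety is a recognizable choice. Safety reporting is descriptive, so no test or error rate is affected. At these sample sizes the counts are probably small enough to read from a listing.

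Much of this stands, and it rules out two stronger readings.

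- A reader might infer that unconfirmed COVID-19-coded SAEs appear in no between-arm table at all. The SAP does not establish that. An event within 28 days of a dose may still enter the other unsolicited AE tables.
- A reader might infer that serious COVID-19 cannot be compared between arms. Section 7.7.2 does compare hospitalized, ICU and fatal confirmed cases between pooled active and placebo.

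It is also only a possibility that a serious vaccine reaction would keep a suspected COVID-19 term after two negative swabs. Nothing in the SAP suggests this would be common.

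The reply does not remove the conflict. Section 7.6.3 itself plans numbers and percentages of participants, and a listing does not give those. Harm monitoring for the DRC is not the reported safety analysis by regimen. A wish to separate the target disease is no reason to exclude events never confirmed as that disease.

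**Conclusion.** The point holds in this limited form. Sections 7.3, 7.1.2 and 7.6.2 define and tabulate SAEs without a COVID-19 exception, and section 7.6.3 makes one by Preferred Term. The resulting SAE incidence by regimen is incomplete for a primary endpoint. Unconfirmed COVID-19-coded SAEs are counted as SAEs in no planned table by regimen, and beyond 28 days after a dose they have no AE table. Confirmed serious cases lose their seriousness in the tables by regimen and are compared only in pooled monitoring.

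This rests on two readings: that the exclusion also covers the SAE line of the AE summary table, and that section 7.7.3 is the full extent of the separate analysis. The number of affected events is unknown, so no size of bias can be stated beyond the weight per participant given above. The data survive in the listings, so the defect lies in the tabulation and should be corrected in the plan.

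**What to change.** 1. In section 7.6.3, tabulate all SAEs by regimen for the primary endpoint, including those with COVID-19 terms.
2. Keep a COVID-19-excluded SAE table as supplementary, and exclude from it only SAEs with molecularly confirmed SARS-CoV-2.
3. In section 7.7.3, add a row by regimen for serious and for fatal confirmed COVID-19.
4. State in one sentence whether COVID-19-coded SAEs within 28 days of a dose enter the other unsolicited AE tables and the summary table.

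With the first change in place, a later revision of the term list in the Data Presentation Specifications no longer alters the primary SAE table.

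The cost is one or two descriptive tables from data already in the flagged listings. Where small counts could unblind, they can wait until after unblinding, as section 7.7.1 already provides for potentially unblinding immunogenicity outputs.

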7.6.4. Phase Allocation of Adverse Events

Solicited events are always allocated to the respective Post Dose period.

Step 1: Allocation of events to the periods:

Adverse events in the SDTM database are allocated to periods based on their start date/time. If the start date/time of an event falls between (or on) the start and stop date/time of a period, the AE is attributed to that period (treatment-emergent principle).

- In case of partial start or stop dates (i.e. time and/or day and/or month and/or year missing), the events are allocated to the periods using the available partial information on start and end date; no imputation will be done. If, for instance, the AE start date only month and year are available, these data are compared to the month and year information of the periods. This rule may lead to multiplication of the event as a consequence of its assignment to multiple periods.
- In case of a completely missing end date, the date is imputed by the cut-off date of the analysis for participants still ongoing in the study, and by the end date of the last period for participants who discontinued or completed the trial. In case of a completely missing start date, the event is allocated to the first active treatment phase (post dose 1 period), except if the end date of the AE falls before the start of the first active treatment phase (post dose 1 period).

Step 2: Combination of events:

Overlapping/consecutive events are defined as events of the same participant with the same preferred term which have at least 1 day overlap or for which the start date of an event is 1 day

^a In case this list of terms needs to be revised, the DPS will detail the revised list.

after the end date of the preceding event. Overlapping/consecutive events may be combined into one AE or not, according to the following rules:

- 1) If overlapping/consecutive events start in one of the following periods - Screening or post dose extension (i.e. non-active periods) - followed by an AE in - post-dose period (active period) - they are allocated to their respective periods and are considered as separate events.
- 2) In case overlapping/consecutive events start within a single period, they are considered as one and the same AE. The individual events which contribute to this AE are retained as individual records in the ADaM database but are assigned the same onset, period, and total duration. All related attributes to the AE/phase/period should also be consistent with the new event.
- 3) In case overlapping/consecutive events start in both an active period followed by a non active period, they are allocated to the active period only and are considered as one and the same AE. The individual events which contribute to this AE are retained as individual records in the ADaM database but are assigned the same onset, treatment period, and total duration. All related attributes to the AE/phase/period should also be consistent with the new event.
- 4) In case an active period is followed by another active period, and the overlapping/consecutive events start in both periods, they are allocated to their respective period and are considered as separate AEs. The same rule applies for 2 non-active periods.

Remarks:

1. Events can only be combined into one and the same AE if their start and stop dates are known.
2. In case the completely missing end date is imputed (for period allocation), this date is also considered as a complete date.
3. Time is not considered when determining overlap of events.

7.6.5. Missing Data

Missing AE data will not be imputed. Participants who do not report an event will be considered as participants without an event. An AE with a missing severity or relationship will be considered as an AE reported, but will be considered as not reported for the severity or relationship. For example, an AE with missing severity will be considered as an AE reported for the analysis of any grade, but will be considered as not reported for the analysis of at least grade 3.

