6. POPULATIONS FOR ANALYSIS

For vaccine studies, study intervention assignment will follow the as treated principle: all analyses (including safety, immunogenicity and efficacy analyses) will be analyzed by the actually received vaccine.

Population	Description
All screened participants (ALL)	The “all screened participants” set includes all participants that were screened, regardless of whether they were enrolled and/or randomized.
All randomized participants (ALL RANDOMIZED)	The “all randomized participants” set includes all participants that were randomized to one of the treatment groups.
Full Analyses Set (FAS)	The full analysis set will include all participants with at least one vaccine administration documented.
Per Protocol Immunogenicity Set (PPI)	The per protocol immunogenicity population will include all randomized and vaccinated participants for whom immunogenicity data are available excluding participants with major protocol deviations expecting to impact the immunogenicity outcomes. In addition, samples obtained after missed vaccinations or participants with natural infection occurring after screening (if applicable) will be excluded from the analysis set.
Per Protocol Efficacy Set (PPE)	The per protocol efficacy population will include all randomized participants having received at least 1 vaccination for whom efficacy data concerning endpoint measures are available. All efficacy analyses will be done according to the as treated principle (ie, actually received vaccinations).

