7.3.1. Definition of Endpoint(s)

Solicited AEs are used to assess the reactogenicity of the study vaccine and are predefined local (at the injection site) and systemic events for which the participant is specifically questioned and which are noted by participants in their diary. Unsolicited AEs are all AEs for which the participant is not specifically questioned.

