The following endpoints are defined to examine the immune response in vaccinated individuals after natural infection and to explore other potentially informative biomarkers (eg, those associated with more severe disease):

- Confirmation of SARS-CoV-2 infection by molecular testing
- SARS-CoV-2 neutralizing titers in serum measured by a VNA (wild-type virus and/or pseudovirion expressing S protein)
- SARS-CoV-2-binding antibodies measured by ELISA: Analysis of antibodies binding to the SARS-CoV-2 S protein
- Functional and molecular antibody characterization
- Analysis of gene expression by RNA transcript profiling

7.6. (Other) Safety Analyses

Safety analyses will be performed on the FAS. Continuous variables will be summarized using the following statistics, as appropriate: number of observations, arithmetic mean (mean), standard deviation (SD), standard error (SE), median, quartiles (Q1 and Q3), minimum and maximum. Frequencies and percentages (one decimal place) will be generated for categorical variables. No formal comparisons between groups will be provided.

Safety data will be analyzed by study intervention regimens as designed per protocol^a. In addition, safety data will be analyzed by intervention regimens as designed per protocol and participant seropositivity status at screening. Data will be presented by period (post Dose 1, post Dose 2, post Booster 1, and post Booster 2, as applicable) as well as over the entire regimen, and for Cohorts 2a and 2b over the entire primary regimen and over the entire booster regimen. Denominator for the percentages is the number of participants in the considered population and phase for a certain regimen (incidence per 100 participants/phase).

Exploratory analyses by age (e.g. 18-40 years and 41-55 years) may be performed in Cohort 2.

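### A vaccinated participant with no solicited data from any source after a dose is counted as reaction-free, so this rule can lower the primary reactogenicity percentages but never raise them

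*SAP*

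**What the plan says.** SAP section 7.3 lists as a primary endpoint "Solicited local and systemic adverse events (AEs) for 7 days after each vaccination in the primary regimen". Section 7.3.1 describes solicited events as those "for which the participant is specifically questioned and which are noted by participants in their diary". Unsolicited events are defined there as the ones participants are not asked about.

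Four further statements determine the percentages:

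- Source (section 7.6.2): "Solicited AEs shown in the tables are extracted from the investigator assessment pages (CE) of the CRF".
- Analysis set (section 7.6): "Safety analyses will be performed on the FAS". Section 6 defines that set: "The full analysis set will include all participants with at least one vaccine administration documented".
- Denominator (section 7.6): "Denominator for the percentages is the number of participants in the considered population and phase for a certain regimen".
- Missing data (section 7.6.5): "Missing AE data will not be imputed", followed directly by "Participants who do not report an event will be considered as participants without an event".

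Section 7.6.5 covers adverse events in general. Nothing in the SAP exempts solicited events from its rule or restricts the solicited tables to participants with solicited data after the dose concerned. No table of the number without such data is planned.

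**The concern.** For unsolicited events and SAEs, reading silence as no event is the normal convention, because participants volunteer these events. Solicited events are measured differently. Each participant is asked about each predefined reaction, so a lack of any answer is a missing measurement. The plan treats both situations alike.

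The solicited percentages are a primary result and are reported descriptively, so the reader takes them at face value. A rule that can only move them towards lower reactogenicity is an unfortunate default for a safety endpoint. If the amount of missing data differs between regimens or doses, the descriptive contrast between columns is distorted too. With no count of participants without data, the reader could not judge the size of either effect.

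**Working it through.** The SAP states no solicited event rate and no completion rate, so there is no figure of its own to reproduce. The check is direct arithmetic on assumed values.

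**Step 1: who is affected.** The Post-dose period begins at the vaccination itself (section 7.1.2, Tables 1 to 3). Everyone who receives a dose is therefore in that period's denominator. Someone who misses dose 2 never enters the Post-dose 2 period and is not affected. Because the tables draw on the CE pages, the affected group is participants vaccinated at that dose with neither a diary entry nor a completed CE assessment.

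**Step 2: formulas.** Let m be the fraction of vaccinated participants without solicited data, p the event rate among those with data, and q the unknown rate among those without.

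- Tabulated rate under the SAP: p(1−m)
- True rate: p(1−m) + qm
- Error of the SAP rate: −qm, which is zero or negative
- Relative shortfall: qm / [p(1−m) + qm], which equals m when q = p

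**Step 3: size when q = p** (p and m assumed):

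| p | m = 2% | m = 5% | m = 10% | m = 20% |
|---|---|---|---|---|
| 10% | 9.8% | 9.5% | 9.0% | 8.0% |
| 30% | 29.4% | 28.5% | 27.0% | 24.0% |
| 60% | 58.8% | 57.0% | 54.0% | 48.0% |
| 80% | 78.4% | 76.0% | 72.0% | 64.0% |

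In percentage points the loss is p × m, for example 60% × 10% = 6 points.

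**Step 4: dependence on q** (p = 60%, m = 10%, so the SAP tabulates 54%):

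| q | True rate | Relative shortfall of SAP rate | Rate using only those with data | Its error |
|---|---|---|---|---|
| 0% | 54% | 0% | 60% | +6 points |
| 30% | 57% | 5.3% | 60% | +3 points |
| 60% | 60% | 10% | 60% | 0 |
| 100% | 64% | 15.6% | 60% | −4 points |

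**Step 5: unequal missingness.** Take assumed rates of 60% and 20%, a true difference of 40 points, with q = p in each group.

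- 10% missing in the first group and 2% in the second: 60 × 0.90 − 20 × 0.98 = 54.0 − 19.6 = 34.4 points
- 2% and 10%: 60 × 0.98 − 20 × 0.90 = 58.8 − 18.0 = 40.8 points

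**Step 6: scale in people.** Section 7.7.3 uses 860 active participants. If m were 5% or 10%, that would be 860 × 0.05 = 43 or 860 × 0.10 = 86 people counted as reaction-free without data.

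**The case against.** The strongest objection is that restricting the denominator is not always better. The SAP's error is −qm; the error of a rate based only on those with data is (p−q)m. When q is below p/2 the restricted rate is further from the truth. At p = 60%, m = 10% and q = 30% the two errors are equal and opposite (54% and 60% against 57%). People with nothing to report may well be the ones who return nothing. This arithmetic stands. It argues for showing both percentages and the number without data, not for leaving the SAP's version as the only one. A threshold of one assessment also leaves partly completed diaries in the denominator, which stands as a limit of the fix.

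The size is also wholly assumed. Nothing in the SAP indicates that 5% or 10% of participants would lack data from every source; at 2% the shift on a 60% rate is 1.2 points. Safety is descriptive, so no test or error rate is affected. Output details are left to the Data Presentation Specifications, where counts could be added. But the SAP states an explicit rule, so the correction belongs in the SAP.

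A reader might infer three stronger things, none of which the document supports:

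- That a lost diary alone makes a participant reaction-free. It does not if the investigator recorded the event on the CE page.
- That the percentages are understated by the missing fraction as a matter of fact. That holds only as a relative reduction and only if q = p.
- That section 7.6.5 plainly contradicts itself. Not imputing records while classifying participants by what was reported can be read as one openly stated counting rule. The fair criticism is that, for solicited events, its effect is the same as imputing no event. For the symptom questionnaire in section 7.7.3, by contrast, the SAP leaves an entry unimputed when it is missing for reasons such as simple non-completion.

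**Conclusion.** The point holds in limited form. Followed as written, sections 6, 7.6 and 7.6.5 count vaccinated participants with no solicited data from any source as having had no reaction. The effect on the tabulated rate is −qm: zero if those participants truly had no reactions, otherwise an understatement. With q = p and an assumed m of 2% to 10%, a 60% rate loses 1.2 to 6 points. Over the full range of q at p = 60% and m = 10%, the relative shortfall runs from 0% to 15.6%.

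The direction follows from the SAP alone. The size rests on assumed values of p, q and m, and may be negligible if nearly everyone has a CE assessment after each dose. The distortion of contrasts between regimens depends further on missingness being unequal, for which the SAP offers no evidence either way.

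**What to change.** In section 7.6.5, limit the rule that no report means no event to unsolicited adverse events and SAEs. In section 7.6, state that for solicited event tables:

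- the denominator is FAS participants who received that dose and have at least one solicited assessment (diary or CE page) in the 7-day window;
- the number without data is shown per regimen and dose;
- the percentage over all vaccinated FAS participants is kept as a supporting display.

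The cost is a short SAP change, one denominator flag and one extra row, plus the supporting display. Denominators become slightly smaller and percentages slightly higher. If participants without data react less often than the others, the new percentage may be a little too high; setting the two displays side by side makes that visible. The convention for unsolicited events and SAEs does not change.
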